6.3 Investigator Reporting Responsibilities

The conduct of the study will comply with all FDA safety reporting requirements.

All adverse experience reports must include the patient number, age, sex, weight, severity of reaction (e.g. mild, moderate, severe), relationship to drug (e.g. probably related, unknown relationship, definitely not related), date and time of administration of test medications and all concomitant medications, and medical treatment provided. The investigator is responsible for evaluating all adverse events to determine whether criteria for "serious" and as defined above are present. The investigator is responsible for reporting adverse events to Celgene as described below.

6.3.1 Expedited Reporting by Investigator to Celgene

Serious adverse events (SAE) are defined above. The investigator must inform Celgene in writing using a Celgene SAE form or MEDWATCH 3500A form of any SAE within 24 hours of being aware of the event. The written report must be completed and supplied to Celgene by facsimile within 24 hours/1 business day. The initial report must be as complete as possible, including an assessment of the causal relationship between the event and the investigational product(s), if available. Information not available at the time of the initial report (e.g., an end date for the adverse event or laboratory values received after the report) must be documented on a follow-up report. A final report to document resolution of the SAE is required. The Celgene tracking number (RV-MM-PI-0507) and the institutional protocol number should be included on SAE reports (or on the fax cover letter) sent to Celgene. A copy of the fax transmission confirmation of the SAE report to Celgene should be attached to the SAE and retained with the patient records.

SAEs occurring in patients treated at a participating study site must be reported to Celgene by the respective site investigator within 24h of awareness as outlined above. Copies should be sent at the same time to the principal investigator.

6.3.2 Report of Adverse Events to the Institutional Review Board

The principal Investigator is required to notify his/her Institutional Review Board (IRB) of a serious adverse event according to institutional policy.

6.4 Adverse Event Updates/IND Safety Reports

Celgene shall notify the Investigator via an IND Safety Report of the following information:

- Any AE associated with the use of drug in this study or in other studies that is both serious and unexpected.
- Any finding from tests in laboratory animals that suggests a significant risk for human subjects including reports of mutagenicity, teratogenicity, or carcinogenicity.

The Investigator shall notify his/her IRB/EC promptly of these new serious and unexpected AE(s) or significant risks to subjects.

The Investigator must keep copies of all AE information, including correspondence with Celgene and the IRB/EC, on file (see Section 11.4 for records retention information).

7 Response Criteria

Baseline assessments must occur within \leq 7 days of protocol therapy initiation as indicated in Section 2, Schedule of Study Assessments.

Efficacy assessments are scheduled to occur monthly, beginning at Cycle 3 Day 1, during the first 12 cycles, then every two months.

All response categories (60) require two consecutive blood and urine assessments (bone marrow biopsies do not need to be repeated) and no evidence for progressive or new bone lesions if radiographic studies were performed. Radiographic studies are not required for response assessment but should be obtained when there is clinical suspicion for progressive bone disease.

Complete response (CR)	Negative immunofixation of serum and urine (or normal sFLC ratio if the only measurable disease outside of the bone marrow is by sFLCs) and disappearance of any soft tissue plasmacytomas, and <5% plasma cells in bone marrow
Stringent CR (sCR)	CR as defined above plus normal sFLC ratio and absence of clonal cells in bone marrow by immunohistochemistry or immunofluorescence
Very good partial response (VGPR)	Serum and urine M-component detectable by immunofixation but not on electrophoresis or $\geq 90\%$ or greater reduction in serum M-component plus urine M-component <100mg per 24 h or >90% reduction in the difference between involved and uninvolved serum free light chains if this is the only measurable disease outside of the bone marrow
Partial response (PR)	$\geq 50\%$ reduction of serum M protein and reduction in 24-h urinary M protein by $\geq 90\%$ or to <200mg per 24 h, if the serum and urine M protein are unmeasurable, a $\geq 50\%$ decrease in the difference between involved and uninvolved sFLC levels is required in place of the M protein criteria, if the only measurable disease is in the bone marrow, a $\geq 50\%$ reduction in bone marrow plasma cells is required, provided the baseline percentage was $\geq 30\%$. In addition to the above criteria, if present at baseline, a $\geq 50\%$ reduction in the size of soft tissue plasmacytomas is required.
Minor response (MR)	$\geq 25\%$ but $\leq 49\%$ reduction of serum M protein and reduction in 24 h urine M protein by 50–89%, which still exceeds 200mg per 24 h. In addition to the above criteria, if present at baseline, 25–49% reduction in the size of soft tissue plasmacytomas is also required. No increase in size or number of lytic bone lesions (development of compression fracture does not exclude response).

Stable disease (SD)	Not meeting criteria for sCR, CR, VGPR, PR, MR, or progressive disease (see under 5.9.1).
---------------------	---

8 Protocol Amendments/Deviations

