5.2.1 Inclusion Criteria

Subjects must meet the following inclusion/exclusion criteria to be eligible for the study.

Inclusion Criteria

1. Understand and voluntarily sign an informed consent form.
2. Age ≥ 18 years at the time of signing the informed consent form.
3. Able to adhere to the study visit schedule and other protocol requirements.
4. Refractory or relapsed multiple myeloma (see under 5.3.)
5. Measurable disease defined as at least one of the following: Serum m-spike $\geq 1\text{g/dL}$, urine m-spike $\geq 200\text{mg/24hrs}$, serum free light chains $\geq 100\text{mg/L}$ (provided the kappa/lambda ratio is abnormal), or bone marrow plasma cells $\geq 30\%$.
6. Previous therapy with IMiD™ compounds (thalidomide, lenalidomide, pomalidomide), proteasome inhibitors (bortezomib, carfilzomib), and corticosteroids must be discontinued at least 14 days before entry onto this study.
7. Previous cytotoxic chemotherapy (e.g. alkylating chemotherapy, anthracyclines, and vinca alkaloids), radiation therapy to the pelvis, and any experimental therapy other than carfilzomib or pomalidomide must have been discontinued at least 28 days prior to entry onto this study.
8. ECOG performance status of ≤ 2 at study entry (see Appendix II).
9. Laboratory test results within these ranges:
 - Absolute neutrophil count $\geq 1,500 / \text{mm}^3$
 - Platelet count $\geq 75,000/\text{mm}^3$
 - Calculated creatinine clearance (Cockcroft-Gault) $\geq 30\text{ml/min}$.
 - Total bilirubin $\leq 1.5 \times \text{ULN}$
 - Serum glutamic-oxaloacetic transaminase (SGOT) (aspartate aminotransferase [AST]) and serum glutamic-pyruvic transaminase (SGPT) (alanine aminotransferase [ALT]) levels $\leq 2 \times \text{ULN}$
10. All study participants must be registered into the mandatory RevAssist® program, and be willing and able to comply with the requirements of RevAssist®.
11. Females of childbearing potential (FCBP)† must have a negative serum or urine pregnancy test with a sensitivity of at least 50 mIU/mL within 10 – 14 days prior to and again within 24 hours of prescribing lenalidomide (prescriptions must be filled within 7 days) and must either commit to continued abstinence from

† A female of childbearing potential is a sexually mature woman who: 1) has not undergone a hysterectomy or bilateral oophorectomy; or 2) has not been naturally postmenopausal for at least 24 consecutive months (i.e., has had menses at any time in the preceding 24 consecutive months).

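### The CR row accepts a normal free light chain ratio in place of negative immunofixation, so a patient measurable only by free light chains can be scored CR while a smaller M-protein persists

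*Combined protocol and SAP*

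**What the plan says.** Four places bear on this point.

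- **CR row, Section 7 (Response Criteria).** The laboratory condition is "Negative immunofixation of serum and urine (or normal sFLC ratio if the only measurable disease outside of the bone marrow is by sFLCs"). The row continues "and disappearance of any soft tissue plasmacytomas, and <5% plasma cells in bone marrow".
- **sCR row, Section 7.** This is "CR as defined above plus normal sFLC ratio and absence of clonal cells in bone marrow by immunohistochemistry or immunofluorescence". It has no immunofixation requirement of its own.
- **VGPR row, Section 7.** Its first route is "Serum and urine M-component detectable by immunofixation but not on electrophoresis". Its second is a serum reduction of at least 90% with urine M-protein under 100 mg/24 h. Its third, for patients whose only measurable disease outside the marrow is by sFLC, is a fall of more than 90% in the difference between involved and uninvolved light chains.
- **Inclusion criterion 5, Section 5.2.1.** It begins "Measurable disease defined as at least one of the following" and lists a serum M-spike of 1 g/dL or more, a urine M-spike of 200 mg/24 h or more, sFLC of 100 mg/L or more with an abnormal ratio, or at least 30% marrow plasma cells. Any one suffices.

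Section 10.2.3 reports the response rate (RR), the clinical benefit response rate (CBRR) and best response.

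**The concern.** In the CR row the word joining the two laboratory tests is an alternative, not an addition. For the sFLC-only patient, a normal ratio is enough and immunofixation is no longer consulted. That would do no harm if sFLC-only meant that no intact M-protein was present. Criterion 5 does not say that: it sets thresholds, and a serum M-spike just under 1 g/dL or a urine M-spike just under 200 mg/24 h counts as not measurable although it is there.

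A patient with a residual M-protein can therefore be entered as CR. The response categories then lose their order at the top, because the finding that keeps other patients at VGPR is disregarded for this group. At stake is how deep the reported best responses look. The extension cohort is meant to give an initial impression of efficacy before a larger phase II trial.

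**Working it through.** The plan gives no figure that depends on this clause, so there is nothing to reproduce. The check applies the rows literally to two illustrative records and then does simple arithmetic on the stated group sizes. The patient values are chosen for illustration; the thresholds are the protocol's.

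**Step 1. Can the patient enrol as sFLC-only?** Yes. Under criterion 5, sFLC of at least 100 mg/L with an abnormal ratio is sufficient alone. A serum M-spike below 1 g/dL and a urine M-spike below 200 mg/24 h do not count as measurable.

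**Step 2. Apply the rows.**

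| | Record A | Record B |
|---|---|---|
| Baseline serum M-spike | 0.8 g/dL | 0.5 g/dL |
| Baseline urine M-protein | 50 mg/24 h | below 200 mg/24 h |
| Baseline involved sFLC | 400 mg/L, ratio abnormal | at least 100 mg/L, ratio abnormal |
| On treatment: sFLC ratio | normal | normal |
| On treatment: electrophoresis | M-spike 0.5 g/dL | negative |
| On treatment: immunofixation | positive | positive |
| Marrow plasma cells | 3% | below 5% |
| Soft tissue plasmacytoma | none | none |
| CR row as written | met | met |

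Record A: the serum fall is (0.8 - 0.5)/0.8 = 37.5%. It fails the first VGPR route (the spike shows on electrophoresis) and the second (37.5% is less than 90%). It can be VGPR only by the third route, a fall of more than 90% in the sFLC difference. As written it is CR.

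Record B: this is the finding that the first VGPR route describes, if serum and urine both show it. As written it is also CR.

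**Step 3. Stringent CR.** sCR builds on CR as defined and adds the ratio, which these patients have already used, and absence of clonal marrow cells. Neither record gives a clonality result, so neither shows sCR. With a negative clonality test, both would be sCR despite positive immunofixation.

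**Step 4. Does any other text restore immunofixation?** No. In the Section 2 schedule, footnote 3 adds a marrow examination to confirm CR, and footnote 13 refers back to Section 7.

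**Step 5. Size per patient** (group sizes from Sections 10.2.3 and 10.1).

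- HTLD / HTLD-CKD group of 22: 1/22 = 4.5 percentage points.
- HTLD / HTLD-CKD group of 16: 1/16 = 6.3 percentage points.
- Entire study group, if all 44 are enrolled: 1/44 = 2.3 percentage points.

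**Step 6. Effect on RR and CBRR if CR is tightened.** RR is sCR+CR+VGPR+PR, so it does not change as long as the patient still meets VGPR or PR. Clinical benefit in Section 4.1.2 is minor response or better, and on that definition it does not change either. CBRR as printed in Section 10.2.3 is sCR+CR+VGPR+MR, without PR. A move from CR to PR would lower that printed sum, which is a separate defect.

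**The case against.** **The substitution looks deliberate.** The VGPR and PR rows also let sFLC take over when M-protein is not measurable, and PR says so openly. This stands in part. The documents support calling the CR definition too permissive. They do not support the inference that it is a copying error from the cited criteria, which cannot be checked here.

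**Overlap between rows is normal.** The categories are nested, and a patient who meets CR will often also meet VGPR or PR; reporting the best category resolves that. Agreed: overlap alone proves nothing. What remains is that the specific finding separating VGPR from CR is set aside for one group of patients.

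**sCR is protected by the marrow test.** A reader might infer that sCR follows automatically from the ratio. It does not, because clonal cells must also be absent. The gap in sCR is real but narrower than the gap in CR.

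**Few patients, if any, will be affected.** This stands. One could assume, without support in the documents, that 10-20% of patients are sFLC-only. That gives 0.10 x 16 = 1.6 to 0.20 x 22 = 4.4 patients, but it counts everyone to whom the clause applies. A misclassified patient must also have a sub-threshold M-protein, normalise the ratio, reach under 5% marrow plasma cells, have no plasmacytoma and stay immunofixation-positive. The documents give no rate for any of these. The synopsis describes a median of 4.5 prior regimens, 88% refractory to lenalidomide, and clinical benefit in 40% on twice-weekly dosing, so deep responses may be rare.

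**Immunofixation may not always be done.** Section 2 lists serum and urine immunofixation in the same row as the sFLC assay, but the synopsis and Section 4.2.2 call for it only as appropriate. The fix has to cover this.

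**Conclusion.** The point holds as a minor defect of definition. Followed literally, the CR row can classify a patient with a persisting sub-threshold M-protein as CR, or as sCR if the marrow shows no clonal cells, in conflict with the VGPR row.

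The size is 4.5 to 6.3 percentage points in the CR/sCR proportion per affected patient among the 16-22 at the HTLD / HTLD-CKD. The number of affected patients is unknown and may be zero. The conclusion rests on reading measurable as criterion 5 defines it, which is the only definition of measurable disease in the protocol.

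A reader might infer that the trial's efficacy conclusions are overstated. The documents do not support that. The primary endpoint rests on dose-limiting toxicity, the named response endpoints are PR or better and minor response or better, and no test or stopping rule uses the CR rate. Nor can it be said without qualification that both summary rates are untouched: RR is, if VGPR or PR is still met, but CBRR as printed could fall.

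**What to change.** In the CR row of Section 7, make the ratio an additional condition: serum and urine immunofixation must both be negative for every CR, and where sFLC is the only measurable disease outside the marrow, the sFLC ratio must be normal as well. The marrow and plasmacytoma conditions stay. sCR then inherits the corrected rule.

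State that a patient with a normal ratio but positive immunofixation is scored under VGPR or PR. Record A becomes VGPR if the sFLC difference has fallen by more than 90%, otherwise PR if it has fallen by at least 50%. Record B becomes VGPR by the first or third route, otherwise PR.

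Add that serum and urine immunofixation results must be available whenever CR is declared, so that the as-appropriate wording in the synopsis and Section 4.2.2 does not leave the criterion untested.

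The cost is one clause and one clarifying sentence. Both tests are already in the Section 2 panel, so no new type of test is needed, and patients with results on file can be rescored. The reported CR rate may become slightly lower.

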
STUDY OBJECTIVES:

Primary:

- Define the highest tolerated low doses (HTLD and HTLD-CKD for GFR > 60 ml/min and 30-59ml/min, respectively) and safety of azacitidine given at low but increasing doses up to 50mg/m² twice a week concurrently with GFR-adjusted lenalidomide doses and low dose dexamethasone in patients with relapsed or refractory multiple myeloma.

Secondary:

- Response according to international response criteria (\geq PR) and clinical benefit response (\geq minor response according to adapted EBMT criteria), see under 7
- Correlate response with plasma activity of the azacitidine inactivating enzyme cytidine deaminase (CDA)
- Progression-free survival and overall survival
- Peripheral blood hematopoietic progenitor (CD34+) yield and time to neutrophil and platelet recovery in patients undergoing autologous stem cell transplantation
- Promoter demethylation and gene reactivation in myeloma cells and hematopoietic progenitors treated at the HTLD / HTLD-CKD level after one cycle of therapy
- Changes in global gene expression in myeloma cells treated at the HTLD / HTLD-CKD level after one cycle of therapy

STUDY DESIGN:

Two institutions phase I/II study, classical 3x3 design for patients with GFR \geq 60ml/min, modified 3x3 design for patients with GFR 30-59ml/min, with 10 additional patients treated at the highest tolerated low dose (HTLD / HTLD-CKD).

Patient population: Multiple myeloma, with relapsed or refractory disease (see under 5.3).

The Cockcroft-Gault formula will be used for all GFR estimations throughout this study (Appendix IV).

STUDY ENDPOINTS**Primary:**

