5.9.1 Progressive Disease

Progressive disease (PD) is defined according to the international uniform response criteria (Durie et al. Leukemia 20:1467-73, 2006, ERRATUM Durie et al. Leukemia 21:1134, 2007) and requires any of the following, confirmed on two consecutive assessments:

An increase of 25% from lowest response value in any one or more of the following:

- Serum M-component (absolute increase must be ≥ 0.5 g/100 ml) *
- Urine M-component (absolute increase must be ≥ 200 mg per 24 h)
- Only in patients without measurable serum and urine M-protein levels: the difference between involved and uninvolved FLC levels (absolute increase must be >100 mg/l)
- Bone marrow plasma cell percentage (absolute % must be $\geq 10\%$)

And / or:

- Definite development of new bone lesions or soft tissue plasmacytomas or definite increase in the size of existing bone lesions or soft tissue plasmacytomas
- Development of hypercalcemia (corrected serum calcium >11.5 mg/100 ml) that can be attributed solely to the plasma cell proliferative disorder

*: If the starting serum m-protein level is ≥ 5 g/dL an absolute increase of ≥ 1 g/dL, verified on two consecutive measurements, is sufficient to define progressive disease.

The decision as to when to repeat the assessment to document progressive disease will be left at the discretion of the treating physician, there is no need to wait until the next scheduled response assessment.

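### Section 7 caps minor response from above: read literally, a patient who meets every MR floor, overshoots one band and misses PR is scored stable disease

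*Combined protocol and SAP*

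**What the plan says.** Section 7 (Response Criteria) defines three categories that matter here.

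- **MR.** A serum fall of at least 25% and at most 49%, joined by *and* to the urine limb: "reduction of serum M protein and reduction in 24 h urine M protein by 50–89%, which still exceeds 200mg per 24 h". For plasmacytomas: "if present at baseline, 25–49% reduction in the size of soft tissue plasmacytomas is also required".
- **PR.** A serum fall of at least 50% and a urine fall of at least 90% or to below 200 mg/24 h. Plasmacytomas present at baseline must shrink by at least 50%.
- **SD.** The residual category: "Not meeting criteria for sCR, CR, VGPR, PR, MR, or progressive disease".

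Progression is defined in Section 5.9.1: "An increase of 25% from lowest response value in any one or more of the following", with absolute minimum increases.

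The Synopsis and Section 4.1.2 make clinical benefit response a secondary objective, set at or above "minor response according to adapted EBMT criteria". Section 10.2.3 analyses the CBRR in the entire group and in the 16–22 patients at the HTLD / HTLD-CKD. No section says that a result above the MR band in one limb still counts as MR.

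**The concern.** A response scale should not rank a larger reduction below a smaller one. PR needs every limb to reach its threshold, while MR needs every limb to stay inside a band. A patient with one limb at PR depth and another at MR depth fits neither, and the residual rule then makes that patient SD.

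At stake is the CBRR. Under the literal rule, patients with discordant serum and urine responses leave its numerator, and the split between MR and SD no longer follows tumor reduction. If some assessors apply the bands literally and others treat the categories as ordered, the rate depends on who scores it. The trial has two institutions.

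**Working it through.** **Inputs.** Band limits and PR thresholds are from Section 7, the progression rule is from Section 5.9.1, and the denominators are from the Synopsis and Section 10.2.3. The percentage falls and baseline urine values in the examples are illustrative; the documents give no distribution for them.

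**Notation.** s and u are the percentage falls in serum and urine M protein, B is baseline urine in mg/24 h, and the residual is R = B × (1 − u/100).

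- MR, literal: 25 ≤ s ≤ 49 and 50 ≤ u ≤ 89 and R > 200.
- PR: s ≥ 50 and (u ≥ 90 or R < 200).
- SD: none of the categories, and no progression.

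**Who is affected.** Take patients with s ≥ 25 and u ≥ 50 who do not meet PR.

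- If s ≥ 50, missing PR means u < 90 and R ≥ 200. MR fails because s > 49, so the patient is SD.
- If 25 ≤ s < 50, PR fails on serum. MR also fails whenever u > 89 or R ≤ 200, so the patient is SD.

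**Worked cases.**

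| B | s | u | R | Literal category | Reason |
|---|---|---|---|---|---|
| 1500 | 30 | 70 | 450 | MR | all limbs in band |
| 1500 | 55 | 70 | 450 | SD | serum above 49% |
| 1500 | 30 | 95 | 75 | SD | urine above 89% |
| 3000 | 95 | 85 | 450 | SD | serum above 49%; urine misses PR |
| 1000 | 40 | 82 | 180 | SD | residual not above 200 |
| 1000 | 60 | 40 | 600 | SD | urine below the MR floor; caps irrelevant |
| 1000 | 60 | −30 | 1300 | Progression, if confirmed | urine up 30% and 300 mg |

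Rows 1 and 2 show the fault: with urine unchanged, a larger serum fall lowers the category. The plasmacytoma cap acts the same way. Row 1 with a plasmacytoma that shrinks by 60% becomes SD.

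**Two further consequences of the limits.**

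- Serum falls between 49% and 50%, and urine falls between 89% and 90%, lie in gaps between MR and PR.
- A 50% fall from B = 400 leaves 400 × 0.5 = 200, which does not exceed 200. With baseline urine of 400 mg/24 h or less, the literal MR urine limb cannot be met, although Section 5.2.1 accepts 200 mg/24 h as measurable.

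**Size per patient.** The stated denominators reproduce: 6 + 10 = 16 and 6 + 6 + 10 = 22. For the maximum, 18 started + 4 to complete dose level 5 + 12 with reduced GFR + 10 in the extension = 44. One patient moved from MR to SD changes the CBRR by 1/16 = 6.3 points, 1/22 = 4.5 points or 1/44 = 2.3 points.

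**The case against.** **The categories are meant to be ordered.** The objective is worded as MR or better, and Section 5.7.2 speaks of reaching MR or PR range. An assessor might well count serum −55% with urine −70% as clinical benefit. This stands in part: the downward bias exists only if the bands are applied as written, and the documents do not show that they are. It does not remove the conflict between the Section 7 definition and the endpoint.

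**The bands come from published criteria.** Section 7 cites a source for its categories, and the objective refers to adapted EBMT criteria. Neither source is available here. It stands that a revised rule may differ from them and cost some comparability. The protocol's own text still governs scoring.

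**The consequence is limited.** This stands. The primary endpoint rests on dose-limiting toxicity, the response rate at PR or better is unaffected, and the CBRR carries no test or threshold. The stated aim is an initial impression of efficacy.

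**Stronger readings that the documents do not support.**

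- A reader might infer that everyone better than MR in one limb who misses PR in the other is SD because of the caps. The last two table rows show otherwise: one is SD with or without caps, the other is progression.
- A reader might infer that most minor responders are lost. Any such share needs the joint distribution of serum and urine falls and the fraction of patients measurable in both. The documents give neither, and Section 5.2.1 requires only one of four measurable-disease routes.
- A reader might infer that the clinical benefit rates quoted in the Synopsis (40% versus less than 15%) are distorted. The documents do not say how those patients were scored.

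**Conclusion.** The point holds for a defined group: patients who meet the MR floor in every applicable limb, exceed the band in at least one, do not meet PR and have not progressed. Read literally, Section 7 scores them SD, below patients with smaller reductions, against an endpoint of MR or better.

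If the rule is applied literally, the CBRR is biased low by the per-patient amounts shown above. The number of such patients is unknown, so no total bias can be stated. These sizes take the CBRR as MR or better, as the objectives do. The printed formula in Section 10.2.3 leaves out PR, which is a separate matter, as is the lack of a free-light-chain or marrow-only route to MR.

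The change is worth making because the scoring conflict is real and the correction is small, but it concerns a descriptive secondary endpoint.

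**What to change.** Rewrite MR in Section 7 as a hierarchical category with no upper limits:

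- PR or better not met, and no progressive disease;
- serum reduction ≥25%;
- urine reduction ≥50% or to <200 mg/24 h;
- plasmacytoma reduction ≥25% where present at baseline.

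The existing lytic-lesion condition and the requirement for two consecutive assessments stay. The second urine route is needed: serum −30% with urine from 300 to 190 mg/24 h is a fall of 110/300 = 37%. That meets the PR urine limb, yet it would remain SD under a 50% floor alone.

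Costs:

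- Patients already assessed, including the eighteen who started before amendment 7, need re-scoring from serum and urine values already collected. No new measurements are needed.
- The rule may differ from the cited criteria. Reporting the CBRR by the literal bands as well keeps comparability and shows how many patients the change moves.
- Section 5.7.2 uses MR range in a decision on azacitidine dose and must be reconciled with the revised definition. No dosing rule is proposed here.
- Section 5.3.1 uses the Section 7 definition of SD to classify refractory disease, so it should state which definition applies to prior therapy.
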